#### **6.4.5 Other concomitant treatment**

The investigator should instruct the patient to notify the study site staff of any changes in concomitant medications (new medications or changes in dose regimens of existing medications). All concomitant medications and significant non-drug therapies (including physical therapy and blood transfusions) administered after the patient starts treatment with the study medication must be listed on the Concomitant Medications/Significant Non-Drug Therapies electronic case report form.

##### **ACEIs and ARBs**

Patients pre-study ACEIs/ARBs will be replaced with the study medications.

The concomitant use of other ACEIs or ARBs is strictly prohibited while the patient is receiving study medication, regardless of study period (Outpatient dose titration and follow-up). If the investigator believes that addition of an ACEI or ARB is necessary, then study drug must be discontinued. If not already treated with an aldosterone antagonist, consideration should be given to adding this therapy rather than an ACEI or ARB.

##### **Secondary prevention drugs for coronary heart disease and other cardiovascular medications**

The patient should be on an optimal medical regimen of background AMI medications. Medications after PCI also include: dual antiplatelet, statins, beta blockers and so on. The use of mineralocorticoid receptor antagonist (MRA), diuretics and inotropes according to the patient's condition. Every effort should be made to keep the dose level of these background, life-saving AMI medications stable throughout the entire study. However, if the patient's condition warrants a change in any of these medications, it is allowed at the discretion of the study investigator.

Diuretics may be used and may be adjusted throughout the length of the study at the discretion of the investigator.

If a patient experiences any adverse events that may be contributed to the study drug, other Secondary prevention drugs for coronary heart disease, or other CV medications, the investigator should adjust non-life saving medications (e.g., CCBs, nitrates, a-blockers, and diuretics) first in an attempt to alleviate the adverse events.

#### **Medications known to raise potassium levels**

Potassium-sparing diuretics, potassium supplements, aldosterone antagonists, renin inhibitors, and any other medications known to raise potassium levels should be used with caution while the patient is receiving the study medication due to the increased possibility of occurrence of hyperkalemia. The investigator is encouraged to assess patients' potassium levels regularly, especially in those who are receiving these medications.

#### **6.4.6 Study drug discontinuation and premature patient withdrawal**

The emergence of the following circumstances will require study drug discontinuation:

- Withdrawal of informed consent
- Pregnancy (Section 8.3)
- Investigator thinks that continuation would be detrimental to the patient's well-being
- Suspected occurrence of angioedema during the outpatient dose titration and follow-up period

Study medication may be discontinued at the investigator's discretion if any of the following occurs:

- Any severe suspected drug related adverse event
- Suspected occurrence of angioedema. A patient with any signs or symptoms of clinically significant angioedema should be thoroughly evaluated by the investigator and constitute a reason for interruption of study medication.
- Depending on the serum potassium, blood pressure, or eGFR, patients may need to have their study drug dose or the dose of another concomitant medication reduced or discontinued, or, if appropriate, have potentially contributing agents adjusted. Please refer to Appendices 2, 3, and 4 for treatment guidelines for hyperkalemia, hypotension, or renal dysfunction, respectively.

In the case of study drug discontinuation, the patient should continue to complete all scheduled study visits and procedures. If the patient refuses, he/she should be contacted by telephone in place of protocol-specified visits unless the patient expressly refuses such contacts.

The investigator must also record the discontinuation of the drug administration form of the electronic case report form.

#### **6.4.7 Study completion and post-study treatment**

At the end of study visit, patients will decide for themselves whether to continue the drug study. There is no extension study planned after all assessments of the end-of-study visit are completed.

The investigator also must provide follow-up medical care for all patients who are prematurely withdrawn from the study, or must refer them for appropriate ongoing care.

## **7 Visit schedule and assessments**

All patients, including those who discontinue the study medication before completing the study, should continue attending the scheduled visits as outlined in Table 7-1 until the study ends. At that point all patients will return to the study sites as soon as possible to undergo the end of study visit assessments. If any patient refuses to return for these assessments or is unable to do so, every effort should be made to contact him/her or a knowledgeable informant by telephone to ask if any of the secondary and safety endpoints have occurred at the foreseen visit dates for the remaining duration of the study. Documentation of attempts to contact the patient should be recorded in the patient's record.

All data obtained from the assessments listed in Table 7-1 and described in detail in the subsections below must be supported in the patient's source documentation (e.g., medical charts or patient notes).

Table 7-1 indicates which data remain in source documents only (S), or may be entered directly into the database (D; i.e., these data are considered source documentation and do not require separate source documentation), or are entered into the database from separate source documents (DS). Assessments that generate data for database entry and are recorded on electronic case report forms are listed using the electronic case report form name. Assessments that are transferred to the database electronically (e.g., laboratory data) are listed by test name.

There is a short washout periods (approximately 36 hours for each) during the randomization period to minimize the potential risk of angioedema due to overlapping ACE-NEP inhibition at Visit 2 (Section 7.5.7): after randomization at Visit 2.

For example, if a patient's Visit 2 is on Wednesday, he/she must not take any doses of the enalapril medication after the Tuesday evening dose. The patient will then start to take the first dose of the sacubitril/valsartan medication on Thursday morning.

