### **4.2.2 Randomization**

#### **Visit 2 (Randomization Visit)**

Patients who have met all the inclusion criteria and none of the exclusion criteria at the end of the screening period will be randomized to either enalapril or sacubitril/valsartan in a 1:1 ratio. Patients randomized to enalapril continue to receive enalapril, while

patients randomized to sacubitril/valsartan discontinue enalapril to ensure a minimum 36-hour washout period prior to initiation of ARNi therapy. The first dose of sacubitril/valsartan is followed by 6 hours of monitoring for hypotension. After the condition is stable, patients can be discharged from the hospital at any point in time at the discretion of the clinician-investigator. The starting dose during the in-hospital initiation phase is selected using a dose titration algorithm based on systolic blood pressure (SBP) (Figure 1).

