### **6.4.2 Instructions for prescribing and taking the study drug**

The Second Affiliated Hospital of Nanchang University will supply the investigators with all medications sufficient for the course of the study. Patients will be provided with medication packs containing study drug corresponding to their assigned treatment arm and dose level, sufficient to last until the next scheduled visit.

Patients will be instructed to take their morning study drug doses at approximately 08:00 (8 AM) and their evening study drug doses at approximately 19:00 (7 PM). The study medications should be taken with a glass of water with or without food. If the patient misses taking any study drug dose, he/she should take it as soon as possible, unless if it is almost time for the following scheduled dose. In this case, the patient should skip the missed dose and return back to his/her regular study drug administration schedule.

All dosages prescribed and dispensed to the patient and all dose changes during the study must be recorded on the Dosage Administration Record electronic case report form.

The investigator should promote compliance by instructing the patient to take the study drug exactly as prescribed and by stating that compliance is necessary for the patient's safety and the validity of the study. The patient should be instructed to contact the investigator if he/she is unable to take the study drug as prescribed for any reason.

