### **7.5.7 Angioedema**

Angioedema is a type of abrupt swelling that occurs under the skin and/or mucous membranes and is often localized to the head, neck, throat, and/or tongue, but may occur elsewhere, including the genitalia and intestines. Severe cases may be associated with airway compromise. Although, the mechanism is not fully understood, bradykinin has been implicated as the putative mediator. Therefore, medications that raise the levels of endogenous bradykinin by inhibiting the enzymes responsible for its breakdown, such as ACE, aminopeptidase P, and NEP, may result in this potentially dangerous side effect.

Simultaneous inhibition of multiple breakdown pathways of bradykinin is thought to significantly increase the risk of occurrence of angioedema. Section 4.2.2 details how to avoid the simultaneous inhibition of the ACE and NEP pathways by overlapping exposure to sacubitril/valsartan and enalapril at Visit 2 (randomization). The method outlined in Section 4.2.2 is expected to provide at least 36 hours free of significant simultaneous inhibition of NEP and ACE, thereby minimizing the potential risk of occurrence of angioedema. This 36-hour washout period is expected to present minimal risk to patients.

The procedure for reporting angioedema-like events is outlined in Section 8.5.

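### Sections 4.2.2, 6.3 and 7 contradict each other on whether the enalapril washout starts before or after allocation at Visit 2, so the stated 36-hour minimum is not secured by the text

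*Protocol*

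**What the plan says.** Four sections of the protocol bear on the switch from enalapril to sacubitril/valsartan.

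- **Section 4.2.2** (repeated in the synopsis under Visit 2): "patients randomized to sacubitril/valsartan discontinue enalapril to ensure a minimum 36-hour washout period prior to initiation of ARNi therapy". Patients allocated to enalapril simply stay on it. No last-dose or first-dose time is given.
- **Section 6.3**: the arm is assigned by a telephone call at Visit 2. The hour of the visit is not stated.
- **Section 7**: "There is a short washout periods (approximately 36 hours for each) during the randomization period", placed after randomization at Visit 2. The worked example then reads "if a patient's Visit 2 is on Wednesday, he/she must not take any doses of the enalapril medication after the Tuesday evening dose", and the first sacubitril/valsartan dose follows on Thursday morning.
- **Section 7.5.7**: "The method outlined in Section 4.2.2 is expected to provide at least 36 hours free of significant simultaneous inhibition of NEP and ACE".

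For clock times, Section 6.4.2 has patients "take their morning study drug doses at approximately 08:00 (8 AM) and their evening study drug doses at approximately 19:00 (7 PM"). Section 6.1 lists enalapril among the drugs provided after PCI. Section 4.2.1 has the screening visit consider whether enalapril is part of the immediate post-procedure medication.

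**The concern.** Section 4.2.2 makes stopping enalapril a consequence of allocation. The Section 7 example ends enalapril the evening before the visit at which allocation happens. Apart from that example, nothing tells patients to withhold enalapril before they are randomized. Section 7.5.7 relies on Section 4.2.2 for the overlap-free interval, but the only operational schedule is the Section 7 example, which does not match it.

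The protocol gives avoidance of combined ACE and neprilysin inhibition as the purpose of the washout, and it counts angioedema and hypotension among its safety outcomes. A site that takes its stopping rule from one section and its start time from the other would fall below the protocol's own minimum, and only in the sacubitril/valsartan arm. A site that applies the example to everyone would interrupt enalapril in patients who are supposed to continue it.

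**Working it through.** **Inputs**
- Stated interval: 36 h. It is a minimum in Section 4.2.2, *at least* 36 h in Section 7.5.7, and *approximately* 36 h in Section 7.
- Example: Visit 2 on Wednesday, last enalapril dose Tuesday evening, first sacubitril/valsartan dose Thursday morning (Section 7).
- Dose times: about 08:00 and about 19:00 (Section 6.4.2). These are given for study drug. Applying them to enalapril taken before randomization is an assumption.
- Allocation: at Visit 2, that is, on Wednesday in the example (Section 6.3).

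**Formula**: interval = time of first sacubitril/valsartan dose − time of last enalapril dose.

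**Step 1. The example as written.** Tuesday 19:00 to Thursday 08:00 = 5 + 24 + 8 = 37 h. This meets 36 h with a margin of 37 − 36 = 1 h. If each dose time may move by up to 1 h (an assumption), the range is 35 to 39 h.

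**Step 2. Enalapril stopped only after randomization, example's start kept.** If the Wednesday morning dose is taken before the call, Wednesday 08:00 to Thursday 08:00 = 24 h, which is 36 − 24 = 12 h short. With the same 1 h shifts the range is 22 to 26 h, always below 36 h. If the washout is counted from randomization itself, a call at or after 08:00 on Wednesday also leaves at most 24 h before Thursday 08:00.

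**Step 3. The two readings side by side.**

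| Reading | Interval | Conflict |
|---|---|---|
| All patients omit the Wednesday morning dose, as in the example | about 37 h | Washout starts before allocation, and patients later assigned to enalapril miss a dose, against Section 4.2.2 |
| Only sacubitril/valsartan patients stop, after allocation, with a Thursday morning start | at most about 24 h | Below the minimum in Section 4.2.2 and the floor in Section 7.5.7, and against the example's own bar on the Wednesday dose |

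Unless the call is made before the morning dose, neither reading satisfies Sections 4.2.2, 6.3 and 7 together.

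**The case against.** The strongest reply is that no section, read in full, tells a site to start at 24 h. The example forbids the Wednesday dose and, if obeyed, gives about 37 h. Section 4.2.2, if obeyed in full, delays the first sacubitril/valsartan dose until 36 h have passed, whatever the example says about Thursday. The 24 h case takes its stopping point from one section and its start from another. This stands: the example contains no arithmetic error, and a reader who infers that the protocol instructs a 24-hour switch goes too far.

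Two further points also stand. A randomization call before the morning dose would remove the difficulty, and the hour of Visit 2 is left open. The dose times are approximate and written for study drug, so every hour figure here is conditional on them.

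What the reply does not remove is the contradiction itself. The example's stop point is earlier than the allocation on which Section 4.2.2 makes stopping depend, and earlier than the point where Section 7 places the washout.

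A reader might also infer that the whole sacubitril/valsartan arm is affected (142 / 2 = 71 planned), or that the angioedema and hypotension comparisons are confounded. The documents support neither. They do not say how many patients take enalapril before Visit 2, take a dose that morning, or are then started on Thursday. The figure of 71 is only a ceiling, and any bias is unquantified.

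Section 6.4.5 states that "Patients pre-study ACEIs/ARBs will be replaced with the study medications", while the washout text names only enalapril. How the interval is counted for another ACE inhibitor is a separate question and does not bear on this contradiction.

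**Conclusion.** The point holds as an internal contradiction. Sections 4.2.2 and 6.3 tie the stopping of enalapril to an allocation made at Visit 2, and Section 7 agrees in its general statement but departs from it in its example. On the assumed dose times the example gives about 37 h only with the Visit 2 morning dose withheld, normally before the arm is known. Stopping after randomization with the example's start kept gives at most about 24 h, provided that the call comes at or after the morning dose time and that dose was taken. The number of patients concerned cannot be derived from the protocol.

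The difference between *approximately* and a floor of 36 h is a smaller point of wording. It still matters here because the example's margin over the floor is 1 h on times that are themselves approximate.

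The passages should be reconciled because the protocol presents this step as its protection against angioedema.

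**What to change.** Reconcile Sections 4.2.2, 6.3, 7 and 7.5.7, together with the matching Visit 2 text in the synopsis, so that the point at which enalapril stops, the point at which sacubitril/valsartan starts and the stated interval agree with each other and with the timing of allocation. Describe the interval in the same terms throughout. Correct the weekday example or remove it. The sponsor decides the clinical content.

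The cost is a wording amendment, which under Section 12 needs agreement by the research team and ethics committee approval. The reconciliation itself requires no change to the sample size or the planned analyses.

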**Table 7-1 Assessment schedule**

phase	screening	Randomization	Outpatient dose titration period						Follow-up period											
			1	2	3a	3b	3c	3d	4a	4b	4c	4d	4e							
Visit	D/S*																			
Weeks (w)			-2 to -1w	-1W to -0	2w	4w	6w	8w	10w	12w	16w	20w	24w(EOS)							
Informed consent form	S	x																		
Inclusion/Exclusion criteria 	DS	x 2	(x)																	
Demography/Medical history (including smoking history)	DS	x																		
Cardiovascular disease History	DS	x																		
Diabetes mellitus History	DS	x																		
Physical Exam 	S	x		x	(x)	x	x	x	x	x	x	x	x	x	x	x	x	x	x	x
Height (H) / Weight (W)	DS	H / W		W	W	W	W	W	W	W	W	W	W	W	W	W	W	W	W	W
Vital signs	DS	x	x	x	x	x	x	x	x	x	x	x	x	x	x	x	x	x	x	x
Waist/hip circumference	DS			x																
Onset to balloon, h	DS	x																		
KILLIP Classification	DS	x																		
TIMI flow grade	DS	x																		
Coronary heart disease and CV Medications	DS	x	x	x	x	x	x	x	x	x	x	x	x	x	x	x	x	x	x	x
Concomitant Medications	DS	x	x	x	x	x	x	x	x	x	x	x	x	x	x	x	x	x	x	x
Endpoint information	DS	x	x	x	x	x	x	x	x	x	x	x	x	x	x	x	x	x	x	x
AEs / SAEs	DS	x	(x)	x	x	x	x	x	x	x	x	x	x	x	x	x	x	x	x	x

## **7.1 Information to be collected on screening failures**

Patients may discontinue from the study prior to randomization, prior to any study medication being administered.

If a patient discontinues before entering in the randomization period, only the demographic information and Screening Log entry with the reason for discontinuation should be completed on the electronic case report form. It is not necessary to complete all the required evaluations at the time of discontinuation unless medically indicated.

All required evaluations must be performed and clearly documented in the appropriate electronic case report forms of patients who entered the randomization and received study medication. This information must include demographics, reason for discontinuation, and adverse events and safety data (e.g., hyperkalemia, hypotension, renal dysfunction, and other adverse events).

### **Re-screening**

If a patient is not eligible to enter into the randomization period and screen-fails, the investigator may consider re-screening the patient at a later time if he/she believes that the patient's condition has changed and may potentially be eligible. In this case, a completely new patient number will be allocated to the subject and he/she will need to re-perform all Visit 1 procedures.

## **7.2 Patient demographics/other baseline characteristics**

Patient demographic and baseline characteristic data to be collected on all patients include: date of birth, age, sex and source of patient referral. Relevant medical history/current medical condition data includes data until the start of study drug. Where possible, diagnoses and not symptoms will be recorded.

## **7.3 Treatment exposure and compliance**

Compliance will be assessed by the investigator and/or study personnel at each visit using pill counts and information provided by the care giver. This information should be captured in the source document at each visit. Patient compliance should be at least 80% during the Outpatient dose titration and follow-up period. The investigator and/or study personnel will counsel the patient if compliance is below 80%. Study

drug accountability will also be determined by the site monitor while performing routine outpatient visits and at the completion of the study.

## **7.4 Efficacy**

### **7.4.1 Primary and secondary efficacy outcomes**

The primary outcomes are:

- NT-proBNP
- LVEF
- LVEDV
- LVESV

The secondary composite outcome consists of the following components:

- Death
- Reinfarction
- hospitalization for heart failure or outpatient heart failure
- arrhythmia
- stroke

### **7.4.2 Endpoint Committee**

All of the following events, which could potentially fulfill the criteria for the secondary or other endpoints will be assessed during the study, and reported to the Endpoint Adjudication Committee for adjudication or assessment:

- All death events
- All Reinfarction
- Unplanned hospitalization for heart failure or outpatient heart failure
- All arrhythmia
- Stroke
- Renal dysfunction
- Others

The Endpoint Adjudication Committee will be responsible for classifying all death events and for determining whether pre-specified endpoint criteria were met for the other events. if the investigator suspects an endpoint may have occurred, it is best to report the event to the Endpoint Adjudication Committee for the final determination.

guidelines for AE and SAE as outlined in Section 8.1 and Section 8.2 must be followed, independent from the circumstance that an event is also reported as a suspected study endpoint.

### 7.4.3 Endpoint Definitions

Death includes death classified in any of the following categories:

1. Fatal Myocardial Infarction (MI):

a. Death occurring within 14 days after a documented MI, in which there is no conclusive evidence of any other cause of death. Subjects who are being treated for a MI and who die as a result of complications of the MI (eg, sudden death, pump failure, or cardiogenic shock) will be classified as having had a MI-related death.

b. Autopsy evidence of a recent infarct with no conclusive evidence of any other cause of death.

c. An abrupt death that has characteristics suggestive of an acute infarct but does not meet the definition of a MI. Suggestive characteristics are:

-presentation with acute ischemic symptoms

AND one of the following:

- ECG changes indicative of an acute injury

- abnormal cardiac biomarkers

-other evidence (eg, echocardiography, ventriculography, or scintigraphy) of new ventricular wall motion abnormality

2. Heart Failure:

Death occurring in the context of clinically worsening symptoms and/or signs of heart failure (HF) without evidence of another cause of death.

Death occurring as a complication of the implantation of a ventricular assist device, cardiac transplant, or other surgery primarily for refractory HF.

Death occurring after referral to hospice specifically for progressive HF.

3. Sudden Death:

Death occurring unexpectedly in an otherwise stable subject. Further subclassification of sudden death will be as follows:

a. death witnessed or subject last seen alive <1 hour previously or

b. subject last seen alive  $\geq 1$  hr and < 24 hrs previously

4. Presumed Sudden Death

Death occurring unexpectedly in an otherwise stable subject last seen alive  $\geq 24$  hours previously, with circumstances suggestive of sudden death.

5. Presumed Cardiovascular Death:

Death likely due to a cardiovascular cause in which the available clinical data is insufficient to support a more specific cause of death.

6. Fatal Stroke:

Death occurring as a result of a documented stroke. Where possible, the stroke will be further classified as ischemic (non-hemorrhagic), ischemic (non-hemorrhagic) with hemorrhagic conversion, hemorrhagic, or unknown.

7. Fatal Pulmonary Embolism:

Death occurring as a direct result of a documented pulmonary embolism.

8. Cardiovascular Procedure-Related Death:

Death occurring during a cardiovascular procedure or as a result of complications related to a cardiovascular procedure (e.g. percutaneous coronary intervention), usually within 14 days.

